# LIST OF ABBREVIATIONS

| AE
ANOVA
CFR | Adverse Event
Analysis of Variance
Code of Federal Regulations |
|--------------------|--|
| eCRF               | Electronic Case Report Form  |
| CRO                | Contract Research Organization                                       |
| DCF
EC          | Data Clarification Forms
Ethics Committee                         |
| ED                 | Early Discontinuation  |
| EDC                | Electronic Data Capture  |
| EOT                | End of Treatment   |
| FDA                | Food and Drug Administration   |
| GCP                | Good Clinical Practice   |
| hCG                | Human Chorionic Gonadotropin   |
| HEENT              | Head, Eyes, Ears, Nose and Throat                                    |
| HIPAA              | Health Insurance Portability and Accountability Act                  |
| ICF                | Informed Consent Form  |
| IGA                | Investigator's Global Assessment                                     |
| ICH                | International Conference on Harmonization                            |
| ID                 | Identification   |
| IRB                | Institutional Review Board   |
| IUD                | Intrauterine Device  |
| mITT               | Modified Intent To Treat   |
| NSAID              | Non-Steroidal Anti-Inflammatory Drug                                 |
| OTC                | Over the Counter   |
| SAE                | Serious Adverse Event  |
| US                 | United States  |
| UV                 | Unscheduled Visit  |

## STUDY SYNOPSIS

Protocol Number: ADPS 1602

Title of Study:A MULTI-CENTER, DOUBLE-BLIND, RANDOMIZED, PLACEBO CONTROLLED,
PARALLEL-GROUP STUDY TO EVALUATE THE EFFICACY AND SAFETY OF
[Redacted as ATS55] IN THE TREATMENT OF ACNE VULGARIS

**Sponsor:** Taro Pharmaceuticals U.S.A., Inc.

Treatment Duration: The study treatment period will last for 84 days (12 weeks).

## Investigational Products:

| Test Product: | [Redacted as ATS55] (Taro Pharmaceuticals U.S.A, Inc.) |
|---------------|--|
| 100(1100000.  |  |

Placebo Control: Vehicle of the test product (Taro Pharmaceuticals U.S.A., Inc.)

## Dose and Mode

of Administration: A thin layer of study medication will be applied to cover the entire face and other affected body areas once daily.

**Objectives**: To evaluate the efficacy and safety of [*Redacted as ATS55*] (Taro Pharmaceuticals U.S.A, Inc.) in the treatment of acne vulgaris.

**Design**: Subjects in this randomized, double-blind, placebo controlled, parallel-group, multiple-center study will be randomly assigned in a 1:1 ratio to treatment with the test product or placebo control, respectively.

## Clinical Evaluations will be performed at:

Visit 1: Screening/Baseline Visit (Day 0); Visit 2: Interim Visit (Week 2 / Day 14 ± 4 Days); Visit 3: Interim Visit (Week 4 / Day 28 ± 4 Days); Visit 4: Interim Visit (Week 6 / Day 42 ± 4 Days); Visit 5: Interim Visit (Week 8 / Day 56 ± 4 Days); Visit 6: Interim Visit (Week 10 / Day 70 ± 4 Days); Visit 7: End of Treatment Visit (Week 12 / Day 84 ± 4 Days) Visit 8\*: Follow up phone call (Week 13 / Day 91 ± 4 Days) \*if required for on-going AEs based on PI decision

An Unscheduled Visit is allowed at any time, for any reason, if in the Principal Investigator's opinion it is warranted. If a Subject is discontinued from the study during an Unscheduled Visit, the Unscheduled Visit will be referred to as an Early Discontinuation Visit and all procedures scheduled for Visit 7 will be performed. If the Unscheduled Visit is not an Early Discontinuation Visit (i.e., the Subject will continue to take part in the study), then all procedures will be performed and

treated as an interim visit, with the exception of the collection of Investigational Product and Subject diaries from Subjects.

Subjects will be admitted into the study after informed consent/assent has been obtained, a medical history and physical examination (with vital signs) have been performed and inclusion/exclusion criteria have been met. Subjects must have a clinical diagnosis of acne vulgaris to gualify for inclusion in this study.

Each Subject will be randomly assigned in a double-blind fashion in a 1:1 ratio to treatment with the test product or the placebo control.

At the screening/baseline visit, a physical examination (with vital signs) will be conducted. At each subsequent visit, the following procedures will be performed: counts of the facial comedones (open and closed), papules, pustules, nodules and cysts lesions will be performed, the Investigator's Global Evaluation (IGA) will be performed and the signs and symptoms of irritation will be assessed.

Safety will be assessed by the monitoring of all adverse events and the monitoring of any signs and symptoms of local irritation.

## Study Population:

#### **Inclusion Criteria**

[Redacted]

#### Exclusion Criteria

[Redacted]

#### Number of Subjects:

Approximately 300 Subjects, including approximately 24 in the Subgroup, will be enrolled into the study in a 1:1 ratio to the following study arms:

- [*Redacted as ATS55*] (Taro Pharmaceuticals U.S.A, Inc.)
- Placebo (Vehicle of test product (Taro Pharmaceuticals U.S.A., Inc.)

Approximately equal numbers of male and female subjects will be enrolled to each of the study arms.

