At Visit 1, an informed consent/assent and HIPAA authorization will be obtained from the potential study Subject before any study procedures take place. After the Subject has been consented/assented, the Subject's medical history will then be documented, including the Subject's concomitant medications. A urine pregnancy test will be performed for female Subjects of childbearing potential. All female Subjects are considered to be of childbearing potential unless they are premenarchal, have been surgically sterilized or have been postmenopausal for at least 1 year. A baseline acne grade will be assigned to the Subject using the Investigator's Global Assessment (IGA) and a baseline lesion count will be performed. The Subject will undergo a brief physical examination, including the recording of vital signs. The Subject will be evaluated for signs and symptoms of local irritation. The Subject will be reviewed against the inclusion/exclusion criteria. Blinded Investigational Product will be dispensed to Subjects who meet all of the inclusion and exclusion criteria using the lowest patient randomization number available at that investigative site. Subjects will be instructed on the application of Investigational Product and completion of Subject diaries. The Investigational Product should not be opened in the clinic. The first application of Investigational Product will be reviewed.

Subjects will return to the study site for visits at Weeks 2, 4, 6, 8, 10, and 12. The Subject's concomitant medications will be reviewed and documented. A urine pregnancy test will be performed for female Subjects of childbearing potential. The Subject will be evaluated for signs and symptoms of local irritation and any adverse events will be documented. The Subject's facial acne will be assessed using the IGA, the Subject's lesions will be counted and these results will be documented. The Subjects are instructed to bring their used Investigational Product and their study diaries to each study visit. Compliance with drug applications will be assessed at each visit. Additional units of Investigational Product will be dispensed and each Subject will receive new diaries during visits at Weeks 2, 4, 6, 8, and 10. In addition, all Investigational Product and diaries will be collected from the Subject during each scheduled visit or the Early Discontinuation Visit.

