## 8.4 Treatment Assignment

The subject study identification number will correspond to a computer-generated randomization schedule assigning that number to one of the three study treatment groups. The randomization scheme will be generated, in blocks of 6, so that the test product and the vehicle (placebo) control are assigned in a 1:1 ratio. The subject numbers at the site will correspond to the order in which subjects are enrolled into the study.

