## 9.2 Sample Size Rationale

The primary statistical analyses of interest are the differences between the Test and the Placebo (Vehicle) treatments in the mITT population for mean inflammatory and non-inflammatory lesion count reductions, and for proportions of subjects with clinical success on the IGA for. In this Phase 2 study, approximately 300 Subjects will be enrolled to obtain at least 286 evaluable in the mITT Subjects (143 in each treatment group).

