## 9.3 Randomization and Unblinding Procedures

Subjects will be randomly assigned in a 1:1 ratio to receive the test product or the vehicle (placebo) control. The randomization assignment will be generated using SAS® by an independent statistician, not involved with the study.

The Drug Labeling, Packaging facility will hold the randomization code throughout the conduct of the study in order to minimize bias. A sealed copy of the randomization scheme (as a scratch off portion of the product label attached to the drug accountability page) will be retained at the study site. In the event of an emergency, the Subject-specific treatment may be identified; however, every effort should be made to maintain the blind. Where possible, the CRO medical monitor should be contacted before breaking the blind for any patient. The Sponsor must be notified in the event the blind is broken.

The treatment assignments will remain blinded until the final database is closed.

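### Approximately equal numbers of men and women are stated for each arm, but no readable allocation or enrolment rule secures this, and the lesion-count model omits sex (minor)

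*Combined protocol and SAP*

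**What the plan says.** The synopsis (Number of Subjects) says that "Approximately equal numbers of male and female subjects will be enrolled to each of the study arms", and Section 4.1 repeats it. Both places write it as something that will happen.

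The allocation is described in three places:

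- Section 8.4: "The randomization scheme will be generated, in blocks of 6", and "The subject numbers at the site will correspond to the order in which subjects are enrolled into the study".
- Section 3: product is dispensed "using the lowest patient randomization number available at that investigative site".
- Section 9.3: "Subjects will be randomly assigned in a 1:1 ratio to receive the test product or the vehicle (placebo) control".

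None of these names sex as a stratification factor, and no readable section sets a quota, cap or target by sex. The efficacy model in the synopsis and Section 9.10 is an ANOVA with treatment and center for the lesion counts, and Fisher's exact test for IGA success. Section 9.8 plans a comparability check of demographic characteristics across the groups; its detail is redacted.

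**The concern.** Two things are needed for each arm to be about half men and half women. Overall enrolment must be about half men, and the randomization must then divide each sex evenly. The readable text provides for neither. Blocks of 6 at a site balance the number of subjects per arm at that site, but they take no account of whether the next subject is a man or a woman.

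What is at stake is limited. A stated feature of the design may not be met, and a chance sex imbalance would enter the lesion-count comparison without adjustment, at some cost in precision and ease of interpretation. Sections 1 and 9.1 say that the results will be used to size Phase 3 and set its endpoints, so avoidable noise carries forward.

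**Working it through.** **Inputs from the documents.** About 300 enrolled (synopsis, Sections 3 and 4.1), 1:1 allocation, hence 150 per arm; blocks of 6 (Section 8.4); about 5 sites (Section 4.1).

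**Assumptions.** Five sites of 60; men and women arrive in random order. Approximately equal is read as 45-55% male in an arm, because the protocol gives no tolerance.

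**The plan's own figure.** Section 9.2 gives 300 enrolled for 286 evaluable: 2 × 143 = 286, and 14/300 = 4.7% loss. The arithmetic is consistent. The effect size, SD and power behind 286 are not stated, so the sample size cannot be rebuilt. The point made here does not depend on it.

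**1. Half of enrolment is male (150 of 300), no sex stratum.** The number of men in one arm is hypergeometric, with mean 75 and variance 150 × 0.5 × 0.5 × 150/299 = 18.8, so SD 4.34.

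- 95% range: 67 to 83 men per arm (44.7% to 55.3%).
- P(arm outside 45-55% male), i.e. 67 or fewer or 83 or more men: 8.3%.
- P(arm outside 40-60% male): 0.03%.

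Simulating blocks of 6 gives the same range and probability, so blocking without a sex stratum does not help here.

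**2. Between-arm difference in number of women.** The simulation lets each subject be a woman with probability one half.

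| Allocation | SD | 95% of trials within | P(difference of 10 or more) |
|---|---|---|---|
| Blocks of 6 within site | about 8.7 | ±17 | 27-28% |
| Blocks of 6 within site and sex | 2.4 | ±5 | below 0.1% |

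Both SDs can be checked by hand. Without a sex stratum, √(300 × 0.25) = 8.66, and 1.96 × 8.66 = 17. With one, only the last incomplete block in each stratum contributes. If r of its 6 places are used, the variance of the difference is r(6 − r)/5. Averaged over r = 0 to 5 this is (0 + 1 + 1.6 + 1.8 + 1.6 + 1)/6 = 1.167. Over five sites the variance is 5.83, and the SD is 2.4.

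For scale, a difference of 10 is 80 against 70 women, or 53% against 47%. A difference of 17 is 17/150 = 11 percentage points between arms, with each arm about 5.5 points from 50%.

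**3. What an imbalance does to the lesion-count comparison.** Let δ be the difference between men and women in mean percent change, and σ the residual SD. The documents give neither. An imbalance of 17 shifts the arm difference by (17/150)δ = 0.113δ. The standard error of that difference is σ√(2/150) = 0.115σ. The shift is therefore about 0.98 × δ/σ standard errors at the 95% limit. With site-by-sex blocks it is (5/150)/0.115 = 0.29 × δ/σ. Unless δ is an appreciable fraction of σ, both are small.

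**4. Enrolment is not half male.** Suppose 40% of 300, that is 120, are men (an assumption). The mean per arm is 60 men (40%), with SD √(150 × 0.4 × 0.6 × 150/299) = 4.25. A given arm falls outside 45-55% male with probability 96%. Both arms cannot be inside: each would need at least 68 men, and 2 × 68 = 136 exceeds 120. Stratifying by sex would give about 60 men in each arm, so the arms would match each other, but neither would be about half male. Only an enrolment target deals with this.

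**The case against.** The sentence says approximately and speaks of enrolment, so it can be read as a recruitment aim that sites manage in practice. Given equal recruitment, 1:1 allocation usually delivers it: 92% of trials keep both arms within 45-55% male, and a difference of 10 women is still approximately equal. That stands, and it is why this is a minor point. It leaves open how recruitment is to be kept equal, on which the readable text says nothing.

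Part of Section 8.3 and all the eligibility criteria are redacted, so a rule by sex could sit there. This cannot be excluded. Sections 8.4 and 9.3, where a stratification factor would be expected, show no redaction and name none.

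Three stronger readings are tempting, and the documents do not support them:

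- *That a chance sex imbalance biases the efficacy tests.* It does not. Allocation is random with respect to sex, and the tests already allow for chance differences between arms.
- *That Section 5.3 shows sex to be prognostic because it requires stable hormonal contraception.* That rule controls changes in hormone use among women through eligibility. It says nothing about how men and women differ in lesion change or IGA success.
- *That the Subgroup needs its own balanced allocation.* The synopsis mentions "Approximately 300 Subjects, including approximately 24 in the Subgroup", but no section promises an even split of those subjects between arms. Their body-area analysis is descriptive and for information, and the readable text does not define the Subgroup.

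**Conclusion.** The point holds as a minor one. The protocol twice states a sex balance within each arm, and no readable rule delivers it. With equal recruitment the shortfall is small: about 8% of trials have an arm outside 45-55% male, and the 95% range for the difference in women is ±17 where ±5 is attainable. With uneven recruitment the statement almost surely fails; at an assumed 40% male it cannot hold in both arms. The consequence is for the stated property and for precision, not for validity or type I error. The gain in precision depends on an unstated sex effect and is small unless sex is clearly prognostic.

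The figures rest on five sites of 60, random order of arrival by sex, and the 45-55% reading of approximately equal.

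**What to change.** In Sections 8.4 and 9.3, generate the blocked list stratified by sex within site. State an enrolment target by sex, about 150 of each, that matches the synopsis and Section 4.1. Add sex to the lesion-count ANOVA next to center (synopsis and Section 9.10), so that the analysis uses the balance that the list provides. This term does nothing for the IGA comparison by Fisher's exact test, which can stay as planned.

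If the sponsor prefers to leave the list alone, reword the sentence in the synopsis and Section 4.1 as an expectation.

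The cost is about 10 short lists (5 sites × 2 sexes) instead of 5, prepared before first enrolment, and one model term for a variable already collected. Recruitment may slow slightly near the end as one sex reaches its target. Section 8.4 has to be edited in any case, because it refers to three treatment groups in a two-arm trial.

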## Criteria for Evaluation:

#### Endpoints:

- 1) Percent change from baseline to weeks 2, 4, 6, 8, 10, and 12 in the inflammatory (papules and pustules) lesion counts on the face;
- 2) Percent change from baseline to weeks 2, 4, 6, 8, 10, and 12 in the non-inflammatory (open and closed comedones) lesion counts on the face;
- The proportion of Subjects with a clinical response (IGA) of "success" at weeks 2, 4, 6, 8, 10, and 12 on the face. Success is defined as an IGA score that is at least 2 grades less than the baseline assessment.

## Measures:

Lesion Counts will be performed using the following definitions:

## Table 2: Definition of inflammatory and non-inflamatory lesions

<sup>1 http://www.nlm.nih.gov/medlineplus/ency/encyclopedia\_C.htm

| Lesion Type        | Definition  |
|--------------------|---|
| Closed
Comedone | Non-inflammatory lesion; white, raised bumps caused by collections of oil and skin in pores. Also known as white heads and pimples                |
| Open
Comedone   | Non-inflammatory lesion; tiny, dark spots caused by a small plug in the opening of a follicle (pore) on the skin. Also known as blackheads |
| Papule             | Inflammatory lesion; raised spot on the skin that is less than 1 centimeter wide  |
| Pustule            | Inflammatory lesion; small, inflamed, pus-filled , blister-like lesions on the skin surface  |
| Nodules            | Large, hard bumps under the skin's surface  |
| Cysts              | A closed pocket or pouch of tissue. It can be filled with air, fluid, pus, or other material  |

The Investigator's Global Assessment (IGA) will be performed and documented using the definitions in Table 1 (above).

Application site reactions [*Redacted*]will be recorded at each visit to allow a comparison between treatment groups. A detailed scale is presented in Section 5.5.

## Statistical Methods:

#### Efficacy Analyses

The efficacy assessment, superiority will be evaluated for each lesion type on the face using Analysis of Variance (ANOVA), with a statistical model containing terms for treatment and center, and with hypothesis testing at  $\alpha = 0.05$ . The analyses will evaluate if the mean percent change (reduction) from baseline, in each lesion type, for the Test treatment differs from that of the Vehicle. In case of extreme departure from the assumptions of normal error, defined as skewness of residuals from ANOVA model exceeding 2 in absolute value, a ranked-based, nonparametric method will be used. Superiority will be established If the mean percent change (reduction) from baseline for the Test treatment, for each of the inflammatory and non-inflammatory lesion counts is greater than, and statistically different from (p<0.05), that for the Vehicle (Placebo) Control. For the proportions of subjects with treatment success on the IGA on the face the analysis will be conducted using two-sided,  $\alpha = 0.05$  Fisher's exact test. Superiority will be established if the success proportion for the Test treatment is greater than, and statistically different from (p<0.05), that of the Vehicle.

In order to preserve an overall type-I error (alpha) of 5%, a hierarchical evaluation scheme will be employed. The comparisons of interest are:

- 1. percent change from baseline in the inflammatory lesion counts
- 2. percent change from baseline in the non-inflammatory lesion counts
- 3. proportions of subjects with treatment success on the IGA

These comparisons will be performed insequence for weeks 12, 10, 8, 6, 4, and 2.

Statistical testing will begin with comparison 1. If statistical significance is attained with comparison 1 (p < 0.05), then a claim of superiority for comparison 1 can be made and the next comparison in the hierarchical evaluation scheme can be tested for statistical significance. If statistical significance is not attained for comparison 1 (p ≥ 0.05), then testing of all subsequent comparisons is stopped. The hierarchical, conditional-stepwise evaluation scheme allows for each comparison to be evaluated at the 5% level, while preserving an overall type I error rate of no more than 5%.

For **Subgroup** descriptive analyses comparing each lesion type and proportion of subjects with the treatment success on the body will be conducted for information purpose.

Efficacy results will be used to calculate the sample size for the Phase 3 studies.

#### Analysis of application site reactions

A descriptive analysis comparing the application site reactions for each treatment group will be conducted with regard to the expected and unexpected application site reactions. Application sete reactions will also be compared between applications on the face and on the body.

#### Summary of Subjects who terminate prematurely

Reasons for premature termination will be summarized by treatment group.

#### Concomitant medication

The start and stop date of concomitant medication use during the study will be provided in the data set in addition to the reason for the medication use.

#### Safety Analyses

Safety analyses will be conducted on the safety population. Safety Incidence of all adverse events reported during the study will be summarized using the MedDRA dictionary by treatment group, body system, severity and relationship to study drug.

The report of AEs will include date of onset, description of the AE, and date of resolution. Formal statistical evaluation(s) of the comparability of the two treatment groups will be conducted with regard to the frequency and severity of any AE that occurs in at least 5% of the subjects in either treatment group.

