## 9.4 Significance Level

All statistical tests will be two-sided at a significance level of  $\alpha$  = 0.05. No adjustment will be made for multiplicity.

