## 9.9 Safety Assessment

The extent of exposure will be summarized using descriptive statistics. No inferential analyses are planned.

Incidence of all adverse events reported during the study will be summarized using the MedDRA dictionary by treatment group, body system, severity, and relationship to study drug. The comparability of the Test and Placebo treatment groups for the frequency and severity of any adverse event that occurs in at least 5% of the Subjects in either treatment group will be evaluated using categorical methods.

Incidence of concomitant medications will be summarized by treatment group.

Safety analyses will be performed on the safety population. All safety data will be listed by treatment and Subject in data listings.

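### The plan sets out to evaluate adverse-event comparability but supplies only a two-sided 0.05 difference test by an unnamed method, with no margin or confidence interval (minor)

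*Combined protocol and SAP*

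**What the plan says.** The synopsis, under Safety Analyses, states that "Formal statistical evaluation(s) of the comparability of the two treatment groups will be conducted" on the frequency and severity of "any AE that occurs in at least 5% of the subjects in either treatment group". Section 9.9 repeats the plan and says that the comparison "will be evaluated using categorical methods", without naming a test. Fisher's exact test is specified only for IGA success (synopsis and Section 9.10).

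Section 9.4 supplies the only inferential rule: "All statistical tests will be two-sided at a significance level of" 0.05, and "No adjustment will be made for multiplicity".

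No section gives a comparability margin, a confidence interval for a difference in adverse-event incidence, an expected adverse-event rate, or a rule for reading the result.

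Section 9.9 also contains the sentence "No inferential analyses are planned". It closes the short paragraph on extent of exposure, and the adverse-event comparison follows in the next paragraph.

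**The concern.** The stated question and the stated method do not match. Comparability asks whether any difference is small enough not to matter, and answering that needs a margin or at least an interval. A two-sided difference test asks whether the data are incompatible with no difference. Failure to reject is what one expects when the arms are alike, and also when they differ but the sample is too small to show it.

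Section 9.2 sizes the trial by reference to efficacy outcomes only, so nothing in the plan ensures that the adverse-event tests can detect a difference of interest. At stake is how the adverse-event table is read. A p-value alone does not tell the sponsor how large an excess on the test product remains compatible with the data.

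**Working it through.** **Inputs from the documents.** About 300 subjects enrolled, at least 286 of them in the mITT population (Section 9.2). Allocation is 1:1 (Section 9.3), so there are 300/2 = 150 per arm enrolled and 286/2 = 143 per arm in mITT. The safety population needs randomization and at least one dose (Section 9.5), so about 150 per arm is its ceiling; 143 is used as a lower case. Alpha is 0.05, two-sided and unadjusted (Section 9.4).

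**Assumed inputs.** The documents give no adverse-event rates. I take 5% on vehicle, because that is the plan's reporting threshold, against 10% and 15% on test. The test is not named, so both Fisher's exact and the uncorrected chi-square are shown.

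**The plan's own figure.** Section 9.2 states no effect size, SD, rate or power, so the sample size cannot be re-derived; only 2 × 143 = 286 can be confirmed. There is no adverse-event power figure to reproduce.

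**Power by exact enumeration.** For each pair of counts (i, j), take the product of the binomial probabilities Bin(i; n, p_V) × Bin(j; n, p_T), and sum it over the pairs for which the test gives p < 0.05.

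| Vehicle vs test | n per arm | Fisher's exact | Uncorrected chi-square |
|---|---|---|---|
| 5% vs 10% | 143 | 28.0% | 35.2% |
| 5% vs 10% | 150 | 29.8% | 37.0% |
| 5% vs 15% | 143 | 77.3% | 82.3% |
| 5% vs 15% | 150 | 79.7% | 84.3% |

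**Cross-check by normal approximation**, 5% vs 10%, n = 150. The pooled rate is 0.075.
- Null term: √(2 × 0.075 × 0.925) = 0.3725.
- Alternative term: √(0.05 × 0.95 + 0.10 × 0.90) = 0.3708.
- z = (0.05 × √150 − 1.96 × 0.3725) / 0.3708 = −0.317, so power = Φ(−0.317) = 37.5%, in line with the chi-square column.
- By the same approximation, 80% power for 5% vs 10% would need 435 per arm.

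**What an interval adds.** Take 15/150 (10.0%) on test and 7/150 (4.7%) on vehicle as an illustration.
- Tests: Fisher p = 0.12; uncorrected chi-square z = 1.77, p = 0.076. Neither is significant.
- Risk difference: (15 − 7)/150 = 5.3 points.
- Wilson limits: 6.15% to 15.84% on test, 2.28% to 9.32% on vehicle.
- Newcombe lower limit: 5.33 − √[(10.00 − 6.15)² + (9.32 − 4.67)²] = −0.7 points.
- Newcombe upper limit: 5.33 + √[(15.84 − 10.00)² + (4.67 − 2.28)²] = 11.6 points.

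The p-value gives no signal, while the interval shows that an excess of more than 11 points has not been excluded. If both arms showed exactly 5%, the Wald interval would still be ±1.96 × √(2 × 0.05 × 0.95/150) = ±4.9 points.

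**The case against.** The strongest reply is that evaluating comparability may mean no more than comparing the arms. Section 9.8 uses similar language for demographic and baseline characteristics. Section 9.9 also requires incidence by treatment group, body system, severity and relationship, with full listings, so an imbalance such as 15 versus 7 would be visible whatever its p-value. Low power for single adverse events is normal in a Phase 2 trial of 300 subjects. All of this stands, and it limits the weight of the point.

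A reader might infer several stronger things that the documents do not support:

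- *That a non-significant result will be taken as comparable.* No section sets that rule. The wording only leaves room for it.
- *That a non-significant result is uninformative.* Power is about 77 to 84% for 5% versus 15%, so a tripling from 5% would usually be detected.
- *That these tests settle the safety objective, or that their result passes into Phase 3.* Safety also rests on local irritation, application site reactions, exposure and premature terminations. The documents say that efficacy results, not adverse-event comparisons, inform Phase 3.
- *That unadjusted testing will produce many false flags.* The number of events tested is unknown. Ten independent terms at the full 5% would give 1 − 0.95¹⁰ = 40%. Fisher's actual size at 150 per arm is about 2.4% when the true rate is 5%, which gives 1 − 0.976¹⁰ = 22%.
- *That Section 9.9 contradicts the synopsis by ruling out inference.* By position the sentence concerns exposure. Its scope could be clearer, but it is not a demonstrated contradiction.

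What the reply does not remove is that the plan calls the evaluation formal, leaves the test unnamed, and provides no margin or interval.

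**Conclusion.** The point holds as a minor one. The stated method, a two-sided 0.05 difference test of unspecified type, cannot answer the stated question of comparability, and the plan provides nothing else that would.

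The power figures depend on the assumed 5% vehicle rate, on 143 to 150 subjects per arm, and on which categorical test is used. A doubling from 5% is more likely to be missed than found under either test. The consequence is a possible misreading of the adverse-event table, not an error that the plan commits, and no efficacy conclusion changes.

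**What to change.** Make the same change in the synopsis (Safety Analyses) and in Section 9.9:

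1. For each adverse event at or above 5% in either arm, make the risk difference (test minus vehicle) with a two-sided 95% confidence interval the main comparison, and name the interval method, for example Newcombe or Miettinen-Nurminen.
2. Keep the severity comparison as a tabulation of severity by arm, because a single risk difference does not cover it.
3. If p-values are kept, name the test and call them descriptive.
4. State that p ≥ 0.05 is not evidence of comparability.
5. Reword the exposure paragraph of Section 9.9 so that the absence of inferential analyses is tied explicitly to extent of exposure.

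The cost is a wording edit in two places and one extra column in a table already planned. Conduct, sample size and the efficacy analyses do not change.
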